#### 6.1.4. Handling Missing E-diary Data

This section includes missing data handling for e-diary data. For other type of data, the missing data handling methods are provided in the analysis section for the endpoint if applicable.

**For analyses using ANCOVA or mixed model for repeated measures (MMRM)** based on monthly averages the missing data handling methods are as follows:

For patients randomized to active treatment group and did not completed the double-blind treatment period due to lack of efficacy, death, or adverse event, the number of headaches in an analysis window will be imputed as the following

$$\sum (\text{observed headaches during a analysis window}) + (N-X) * (\text{placebo average}/N)$$

Where

$N$  denotes the number of days in the analysis window, 84 days for 12-week analysis window and 28 days for 4-week analysis window;

$X (X > 0)$  denotes the number of days with e-diary within the analysis window;

“Placebo average” is the monthly average of number of headache during the analysis window from placebo patients who completed study.

For 12-week analysis window, the monthly average of the number of headaches will be prorated to 28 days using formula A;

All other missing data for patients in either treatment group will be handled as follows:

- For patients who have  $\geq 10$  days of e-diary data in an analysis window, the monthly average number of headache days will be calculated based on data available in that analysis window and prorated to 28 days using formula A;
- For patients who have  $< 10$  days of e-diary data in an analysis window, the monthly average number of headache days will be imputed using the mean monthly average of headache days in the same analysis window for patients assigned to the same treatment group and having  $\geq 10$  days of e-diary data.

**Note: the imputation is only for post-baseline data and applies to all efficacy endpoints related to the number of headache days.**

In addition, as a sensitivity analysis, the primary endpoint will be analyzed using a MMRM method. Detail is provided in Section 6.2.3.

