**6.1.3. Analysis Windows for E-diary Data**

**Baseline** window is the period from the day of the informed consent to before the administration of the first dose of the IMP. The baseline monthly average value for an efficacy variable will be calculated based on data recorded in the baseline window and prorated to 28 days using formula A.

**Postbaseline 4-week (monthly) analysis windows** will be determined based on the actual dosing date as follows:

- Month 1 (weeks 1 to 4): from the day of the first dose of the IMP administration to the day before the IMP administration at visit 3 (week 4/dose 2) or to the end of e-diary in the double-blind treatment period if a patient only receives dose 1;
- Month 2 (weeks 5 to 8): from the day of the IMP administration at visit 3 (week 4/dose 2) to the day before the IMP administration at visit 4 (week 8/dose 3) or to the end of e-diary in the double-blind treatment period if a patient only receives dose 1 and dose 2;

- Month 3 (weeks 9 to 12): from the day of the IMP administration at visit 4 (week 8/ dose 3) to the end of e-diary of the double-blind treatment period.

Notes:

1. The end of e-diary of the double-blind treatment period is defined as the date of last IMP administration + 27 days.
2. There will be no double-blind IMP administration at visit 5;
3. A 4-week analysis window may contain <28, 28, or >28 days.

The monthly average of an efficacy variable for each analysis window will be calculated based on data recorded in the e-diary and prorated to 28 days using formula A. Missing data handling methods are provided in Section 6.1.4.

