### 6.2.3. Sensitivity Analysis for the Primary Efficacy Endpoint

A sensitivity analysis will be conducted to explore the impact of missing data in the primary efficacy analysis.

MMRM analysis will be utilized to estimate the mean change from baseline (baseline period) in the monthly average number of headache days of at least moderate severity during the 12-week period after the first dose of IMP.

Postbaseline data will include data from 3 monthly analysis windows (Month 1, Month 2, and Month 3) derived using the algorithm described in Section 6.1.3.

The MMRM will include the posttraumatic headache onset (<12 months and  $\geq$ 12 months), treatment, month (3 levels), and month-by-treatment interaction as fixed effects and baseline monthly average number of headache days of at least moderate severity as a covariate. The unstructured covariance structure (UN) will be used to model intra-subject correlation. LS mean and SE for each treatment group, LS means and corresponding 95% confidence intervals for the treatment differences (fremanezumab - placebo), and the associated p-values from the overall results for treatment comparisons on the average of months 1 to 3 will be presented to support the primary analysis. Notes: if UN dose not converge, the hierarchy uses the first-order autoregressive structure [AR-(1)] and the compound-symmetry structure (CS).

Example SAS codes for MMRM analysis:

```
PROC MIXED DATA=<name> METHOD=REML;
  CLASS USUBJID TRTP ONSET AVISIT;
  MODEL CHG=BASE ONSET TRTP AVISIT TRTP*AVISIT/S;
  REPEATED AVISIT/ SUB=USUBJID TYPE=UN;
  LSMEANS TRTP TRTP*AVISIT/ DIFF CL ALPHA=0.05;
  ODS OUTPUT LSMEANS= <name> DIFFS= <name> ;
RUN;
```

Where TRTP denotes the planned treatment group; ONSET denotes the posttraumatic headache onset (<12 months and  $\geq$ 12 months); AVISIT denotes the analysis window; BASE denotes the baseline monthly average number of headache days of at least moderate severity; CHG denotes the change from baseline.

The analysis will be performed on the FAS.

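### The SAP's single-value fill is not switched off for the sensitivity MMRM; if empty months are filled, the only readable missing-data check is somewhat too precise

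*SAP*

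**What the plan says.** - **SAP 6.2.3** gives the MMRM its purpose: "A sensitivity analysis will be conducted to explore the impact of missing data in the primary efficacy analysis". Its monthly values are "derived using the algorithm described in Section 6.1.3", and the overall result, "treatment comparisons on the average of months 1 to 3 will be presented to support the primary analysis". The section does not mention imputation.
- **SAP 6.1.3** defines the monthly windows from actual dosing dates. Month 1 runs to the day before dose 2, or "to the end of e-diary in the double-blind treatment period if a patient only receives dose 1"; Month 2 starts at dose 2 and Month 3 at dose 3. The section ends: "Missing data handling methods are provided in Section 6.1.4".
- **SAP 6.1.4** introduces its rules with "For analyses using ANCOVA or mixed model for repeated measures (MMRM". Active-arm patients who stop for lack of efficacy, death or adverse event get placebo averages for unrecorded days. Otherwise, a window with at least 10 diary days is prorated from the patient's own data, and one with fewer gets the mean of the patient's own arm. In the placebo formula N is "84 days for 12-week analysis window and 28 days for 4-week analysis window", and X, which must exceed zero, "denotes the number of days with e-diary within the analysis window". A bold note applies the imputation to all efficacy endpoints based on headache days. A closing sentence adds the sensitivity MMRM and points to 6.2.3.
- **SAP 6.3.3** analyses the monthly changes by an MMRM analogous to 6.2.3.
- **Protocol 9.5.5.2** asks for an MMRM for the same missing-data purpose and leaves the detail to the SAP.

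**The concern.** An MMRM is useful as a missing-data check because it takes incomplete patients as they are and lets the likelihood use their observed months. If the missing months have already been replaced by arm means, that feature is largely idle. Every inserted value sits exactly on its arm's mean and is counted as a real observation, so the model sees too little spread and too many data points.

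The stake is how the supportive result is read. Agreement with the primary ANCOVA, or a narrower interval, would look like reassurance about missing data when part of it comes from the inserted means. The unsettled text is a second problem: two programmers could build different input data for one prespecified analysis.

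**Working it through.** **1. The text.** 6.2.3 takes its months from 6.1.3, 6.1.3 sends missing data to 6.1.4, and 6.1.4 names MMRM and covers all headache-day endpoints. No sentence breaks this chain. What stays open is whether a month after drop-out exists to be filled:
- *Filled reading:* three calendar months per patient. Empty months count as having fewer than 10 days, and the fixed 28-day N fits this.
- *Dosing reading:* a patient who never receives dose 2 has no Month 2 window. Only windows that were started and left with 1 to 9 diary days are filled.
- On either reading the placebo formula needs X > 0, so it gives no rule for an empty window.

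**2. How the fill differs from the primary.** Take a patient outside the placebo rule who leaves on day 30 after receiving dose 2 on day 29. The 84-day window holds 30 diary days, at least 10, so the primary prorates the patient's own data. In the MMRM, Month 1 is observed, Month 2 has 2 days and gets the own-arm mean, and Month 3 is empty and gets it too on the filled reading.

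**3. Planning inputs** (Protocol 16.1, new wording for Section 9.1): difference 2.0 days, SD 4.4, 80% power, two-sided 0.05, 10% discontinuation. The plan's figure reproduces: 2 × (1.960 + 0.842)² × 4.4² / 2.0² = 76 per arm by the normal approximation. The noncentral t gives power 0.800 at the stated 77, and 154 / 0.90 = 171.1, so 172. Recruitment stopped at 87.

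**4. Simulation.** 44 and 43 patients; REML MMRM with unstructured covariance and the SAP terms; t with 83 df; 10,000 trials per setting (Monte Carlo error about 0.25 points). Assumptions not in the documents: residual SD 4.4 applied to the monthly values, correlation 0.7 between months, baseline SD 5, slope 0.7 on baseline, and the timing and reasons for drop-out. With 5% missing at Month 2 and 10% at Month 3, 87 × 0.05 + 87 × 0.10 = 13 of 87 × 3 = 261 patient-months (5%) are filled.

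Average of Months 1 to 3, no true effect:

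| Handling | Mean SE / empirical SD | Type I error |
|---|---|---|
| All fills own-arm | 0.944 | 6.4% |
| Half of active drop-outs placebo-filled | 0.971 | 5.6% |
| All active drop-outs placebo-filled | 0.998 | 4.8% |
| Observed data only | 0.998 | 5.0% |

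The first row agrees with theory: the critical t with 83 df is 1.989, 1.989 × 0.944 = 1.878, and the two-sided tail beyond 1.878 is 6.4%. Own-arm fills give 6.5% at correlation 0.5 and at 0.85, and 5.8% with missingness halved to 2.5% and 5%. A separately coded simulation of 3,000 trials gave a ratio of 0.950 and 6.3%, against 5.2% on observed data. A third of 3,000 trials gave 7.0% against 5.7%; Monte Carlo error there is about 0.4 points.

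**5. The two readings compared.** 10% of patients leave on a random day from 1 to 84; placebo-rule patients with an empty window are left missing.

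| Reading | Patient-months filled | Own-arm | Half placebo rule |
|---|---|---|---|
| Filled | 11.5 of 261 | 6.1% | 5.7% |
| Dosing | 2.8 of 261 | 5.5% | 5.3% |
| Observed only | 0 | 5.0% | 5.0% |

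**6. Effect on the estimate.** With completely random drop-out, the filled MMRM differs from the 84-day primary by 0.17 days per trial on average, and the observed-data MMRM by 0.04. If drop-outs are about 1 SD worse at Month 1 and the true difference is -2.0, active-arm-only drop-out shifts the own-arm result by 0.16 days towards fremanezumab (0.16 / 2.0 = 8%). The shift is 0.10 if half are placebo-filled and 0.04 if all are. Equal drop-out in both arms gives 0.01, 0.06 and 0.10 days towards placebo. The observed-data MMRM moves by less than 0.01 in every case.

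**The case against.** The best case for the plan is textual. 6.2.3 cites only 6.1.3, whose windows follow actual doses, so a month after drop-out may never arise. The 28-day N appears only in a formula that needs X > 0, so it creates no empty windows. The lead-in's mention of MMRM is needed for 6.3.3 in any case, and the closing sentence of 6.1.4 may have meant a separate, unimputed model. This largely stands: the dosing reading is about as natural as the filled one, and on it the inflation is close to nil. It does not remove the point, because windows with 1 to 9 days are still filled and nothing says which reading applies.

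The size also depends on unseen inputs. The 6.4% needs every active-arm drop-out to be outside the placebo rule, and the 0.16-day shift needs informative drop-out in one arm only. Both limits stand.

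A reader might infer more than the documents support:
- *That the check only repeats the primary.* It does not; step 2 shows that the handling is varied, though mainly by inserting more arm means.
- *That the trial's error rate is inflated.* SAP 7 does not place this analysis in the testing sequence, and nothing here bears on the primary test.
- *That type I error reaches 8 to 12%.* The 3,000-trial simulation gives 8.8% at 20% drop-out, 9.7% at 30%, and 12.2% at 20% plus 10% sparse months, but the plan assumes 10% discontinuation.

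**Conclusion.** The point holds in a limited form. A stated rule, followed as written with empty months filled, makes the sensitivity MMRM about 5% too precise, with type I error about 6 to 6.5% under own-arm fills at 10% discontinuation. It falls to about 5.3 to 5.5% on the dosing reading, and to no inflation if all active-arm drop-outs are placebo-filled, which itself requires a rule for empty windows that the SAP lacks. These figures rest on assumed correlation, timing and reasons for drop-out. The analysis is supportive and carries no decision rule. It is still worth correcting, because this is the one readable analysis assigned to missing data and its input data are not uniquely defined. Confidence is medium.

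**What to change.** - **SAP 6.1.4 and 6.2.3:** state that the sensitivity MMRM uses only observed monthly windows with at least 10 diary days, prorated by formula A. All other months stay missing and no 6.1.4 fill is applied. The result is then the same on either reading of 6.1.3.
- **SAP 6.2.3:** state that the model assumes missing at random, and that it does not carry the primary estimand's placebo-based handling of lack-of-efficacy, death and adverse-event discontinuations. It is to be read beside the primary ANCOVA, not as a test for data missing not at random.
- **SAP 6.3.3:** say which handling applies. The same observed-data fit can supply the monthly contrasts. Keeping the fill there would need a second dataset and a second fit, and would leave the larger Month 3 inflation (7.9% with own-arm fills).

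The cost is a few sentences. The standard error of the 3-month average rises by about 3% (0.858 / 0.830 = 1.034), and the sensitivity analysis gives up the placebo-based penalty, which the primary ANCOVA keeps.

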## 9.5.5.1. Primary Efficacy Analysis

The primary efficacy endpoint for this study will be derived from PTH data (ie, presence of headache [yes/no] and peak severity [mild/moderate/severe]) collected daily using an electronic headache diary application.

The primary endpoint will be analyzed using an analysis of covariance (ANCOVA) method. The model will include treatment as fixed effect and the baseline number of headache days of at least moderate severity and the PTH onset (<12 months and ≥12 months) as covariate. A 95% confidence interval will be constructed for the least squares mean difference between the fremanezumab group and the placebo group, and the p-value will be presented.

The primary estimand for this study is defined by the following attributes:

- The target population includes male and female patients aged 18 to 70 years, inclusive, with a history of PTH (as defined by the ICHD-3 [beta version] criteria).
- The primary outcome measure is the mean change from baseline (baseline period) in the monthly average number of headache days of at least moderate severity during the 12-week period after the first dose of IMP.
- The FAS will be used for efficacy analyses. FAS is a subset of the ITT analysis set and includes only patients who receive at least 1 dose of IMP and have at least 1 postbaseline efficacy assessment on the primary endpoint. In the FAS, treatment will be assigned based on the treatment to which patients were randomized, regardless of which treatment they actually received.
- Treatment effect will be measured via ANCOVA method, including treatment as fixed effect and the baseline number of headache days of at least moderate severity and the PTH onset (<12 months and ≥12 months) as covariates.

For patients assigned to active treatment who discontinue the study due to lack of efficacy, death, or adverse event, the proportion of headache days in the remainder of the analysis window will be imputed as the mean monthly average of headache days in the same analysis window for patients assigned to placebo. All other missing data for patients in either treatment group will be handled as follows:

- For patients who have ≥10 days of e-diary data in an analysis window, the monthly average number of headache days will be calculated based on data available in that analysis window and prorated to 28 days.

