## 1.6. Estimand for Primary Efficacy Endpoint

The primary estimand for this study is defined by the following 4 components:

1. **Target population:** male and female patients aged 18 to 70 years, inclusive, with a history of PTH (as defined by International Classification of Headache Disorders 3rd revision [ICHD-3] (beta version) criteria).
2. **Outcome measure:** mean change from baseline (baseline period) in the monthly average number of headache days of at least moderate severity during the 12 week period after the first dose of the IMP.
3. **Analysis set and handling of intercurrent events:** The full analysis set (FAS) will be used for efficacy analyses. FAS is a subset of the ITT analysis set including only patients who received at least 1 dose of IMP and had at least 1 post-baseline efficacy assessment on the primary endpoint. In the FAS, treatment will be assigned based on the treatment to which patients were randomized, regardless of which treatment they actually received.

For patients randomized to active treatment who did not complete the double-blind treatment period due to lack of efficacy, death, or adverse event, the average number of headache days in the remainder of the analysis window will be imputed as the mean monthly average of headache days in the same analysis window for patients assigned to placebo.

All other missing data for patients in either treatment group will be handled as follows:

- For patients who have  $\geq 10$  days of e-diary data in an analysis window, the monthly average number of headache days will be calculated based on data available in that analysis window and prorated to 28 days
- For patients who have  $< 10$  days of e-diary data in an analysis window, the monthly average number of headache days will be imputed using the mean monthly average of

headache days in the same analysis window for patients assigned to the same treatment group and having  $\geq 10$  days of e-diary data.

More details are provided in Section [6.1.4](#).

4. **Measure of treatment effect:** analysis of covariance model including treatment as fixed effect and the baseline number of headache days of at least moderate severity and the posttraumatic headache onset ( $< 12$  months and  $\geq 12$  months) as covariates.

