**6.1.2. Data Derivation**

The **monthly average** of an efficacy variable will be calculated and prorated to 28 days as follows:

$$\frac{\sum \text{efficacy endpoint data during the period}}{\text{Number of Days with assessments recorded in the eDiary during the period}} \times 28 \text{ [A]}$$

The “efficacy endpoint data” will be “number of headache days of at least moderate severity”, “number of headache days of any severity”, “number of neck pain days of any severity”, “number of days of use of any acute headache medication”, and “number of days associated with use of opioid analgesics for headache” observed during a treatment period.

The “period” will be the baseline period for baseline calculation or 12-week double-blind treatment period or monthly analysis window [eg. Month 1 (weeks 1 to 4), Month 2 (weeks 5 to 8), Month 3 (weeks 9 to 12)] for post-baseline calculations.

The **percentage of reduction** from baseline in the monthly average number of headache days will be calculated as follows:

$$\frac{\text{baseline value} - \text{postbaseline value}}{\text{baseline value}} \times 100\% \text{ [B]}$$

where baseline value and postbaseline value are the monthly average calculated using formula A.

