## 6.2. Primary Efficacy Endpoint and Analysis

### 6.2.1. Definition

The primary efficacy endpoint is the mean change from baseline (baseline period) in the monthly average number of headache days of at least moderate severity during the 12-week period after the first dose of the IMP.

The primary efficacy endpoint for this study will be derived from PTH data (presence of headache [yes/no] and peak severity [mild/moderate/severe]) collected daily using an electronic headache diary application.

Headache days of at least moderate severity will be derived from the e-diary data as described in Section 6.1.1. The 12-week period is the period from administration of the first dose of IMP to the EODBT as defined in Section 4.4. The monthly average number of headache days of at least moderate severity will be calculated using formula A. Missing data handling method is provided in Section 6.1.4.

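### SAP 6.1.4 gives wrong 12-week values for fremanezumab drop-outs: a 28-day placebo average is divided by 84, and the completed total is then prorated over recorded diary days only

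*SAP*

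**What the plan says.** SAP 6.1.4 covers patients randomized to fremanezumab who did not complete the double-blind period because of lack of efficacy, death or adverse event. Their headache count in an analysis window is the observed count plus (N-X) x (placebo average/N), where:

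- the symbol N, for window length, "denotes the number of days in the analysis window, 84 days for 12-week analysis window and 28 days for 4-week analysis window";
- the symbol X is the number of days with diary data in the window;
- the placebo average "is the monthly average of number of headache during the analysis window from placebo patients who completed study".

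For the 12-week window, "the monthly average of the number of headaches will be prorated to 28 days using formula A". Formula A, in SAP 6.1.2, divides by the "Number of Days with assessments recorded in the eDiary during the period" and multiplies by 28. The same section defines a monthly average as a quantity prorated to 28 days.

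The intent is stated in two places. In SAP 1.6 the average for the rest of the window "will be imputed as the mean monthly average of headache days in the same analysis window for patients assigned to placebo". Protocol 9.5.5.1 agrees: "the proportion of headache days in the remainder of the analysis window will be imputed as the mean monthly average of headache days". SAP 1.6 refers to 6.1.4 for the details, and the SAP Introduction says that the SAP prevails over the protocol, so 6.1.4 is the operative text.

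The primary endpoint (SAP 6.2.1) uses both formula A and 6.1.4. A closing note in 6.1.4 says that "the imputation is only for post-baseline data and applies to all efficacy endpoints related to the number of headache days", and SAP 6.3.1 sends the 12-week responder endpoint to the same section.

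**The concern.** There are two faults.

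1. **Scale.** A 28-day quantity divided by 84 is one third of a daily rate.
2. **Denominator.** After imputation the count covers 84 days, but formula A divides by the X recorded days.

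The first pulls the value down and the second pushes it up; they do not cancel in general. The stated intent is met only if the programmer makes two unwritten corrections together: read the placebo average as an 84-day count, and divide by 84.

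The rule applies to one arm only, so its error cannot cancel between arms. It feeds the primary ANCOVA, which is the gate for all later testing in SAP 7. As the text stands, the primary outcome of these patients is not fixed in advance. A programmer has to choose, and the choice determines the direction of the error.

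**Working it through.** **Inputs.** N = 84, the imputation expression and formula A are from SAP 6.1.4 and 6.1.2. The 2.0-day difference, SD 4.4, 10% discontinuation and 77/86 patients per group are from the Section 9.1 wording in Protocol 16.1. Recruitment stopped at 87 patients (Protocol 3.2), so an arm is about 87/2 = 43.5. The documents give no placebo mean, no observed rate, and no number or timing of qualifying exits; those used here are assumptions.

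**The plan's own figure.** There is no worked value for the imputation. The sample size, used here only for scale, reproduces: a two-sample t-test with 2.0/4.4 needs 76.95, so 77 per group, and 77/0.9 = 85.6 gives 86 per group.

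**Formulas.** Let r be the patient's observed rate and P the placebo mean, both per 28 days, and O = rX/28.

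- Intended: I = 28 x [O + (84-X) x P/28] / 84
- SAP total: T = O + (84-X) x P/84
- Reading A, divide by 84: 28T/84. Error against I = -[(84-X)/84] x (2/3)P, which is always negative.
- Reading B, literal formula A: 28T/X. Error against I = [(84-X)/84] x (r + 28P/X - P), which is positive if r > P(1 - 28/X).

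**Neutral check.** If r = P = 10, a sound rule returns 10 at every X. Reading B gives 34.67 at X = 10 (more than 28 headache days in 28 days), 26.67 at X = 14, 16.67 at X = 28 and 11.67 at X = 56. Reading A gives 4.44, 5.56 and 7.78 at X = 14, 28 and 56. In a 4-week window (N = 28, X = 14) the expression gives 5 + 14 x 10/28 = 10, so the one-third fault arises only when N is 84.

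**Illustration, r = 12 and P = 10.**

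| X | O | T | Intended | A: divided by 84 | B: divided by X |
|---|---|---|---|---|---|
| 14 | 6 | 14.33 | 10.33 | 4.78 | 28.67 |
| 28 | 12 | 18.67 | 10.67 | 6.22 | 18.67 |
| 56 | 24 | 27.33 | 11.33 | 9.11 | 13.67 |
| 70 | 30 | 31.67 | 11.67 | 10.56 | 12.67 |

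Reading the placebo average as an 84-day count (3P) gives totals of 31, 32, 34 and 35. Divided by 84 and multiplied by 28, these return the intended values. Divided by X they give 62.00, 32.00, 17.00 and 14.00, so correcting the scale alone is not enough.

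**Direction.** Reading A always lowers headache days and favours fremanezumab. Reading B raises them for every X below 28, and at X = 28 if any headache day was observed. Beyond that it raises them only if r exceeds P/3 at X = 42, P/2 at X = 56 or 0.6P at X = 70. Counter-example: r = 4, P = 12, X = 56 gives T = 8 + 4 = 12, so B = 6.00 against (8 + 12)/3 = 6.67 intended.

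**Responder status.** With a baseline of 12, only X = 14 changes status in the table: the reduction is 14% as intended (10.33) and 60% under reading A (4.78).

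**Shift in the arm mean.** Per-patient errors at P = 10 are -4.44 (A) and +8.00 (B) at X = 28, and -2.22 and +2.33 at X = 56. Dividing by 43.5 gives -0.10 and +0.18, and -0.05 and +0.05.

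| Assumed 2 to 4 qualifying patients | A | B |
|---|---|---|
| X = 28, P = 10 | -0.20 to -0.41 | +0.37 to +0.74 |
| X = 56, P = 10 | -0.10 to -0.20 | +0.11 to +0.21 |
| X = 28, P = 8 to 14 | -0.16 to -0.57 | +0.37 to +0.74 |
| X = 56, P = 8 to 14 | -0.08 to -0.29 | +0.08 to +0.25 |

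For comparison, the standard error of the treatment difference is about 4.4 x sqrt(2/43.5) = 0.94.

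**The case against.** The best defence is that 6.1.4 has a coherent reading. The placebo average is taken over the analysis window, it is divided by that window's N, and a separate sentence for the 12-week window brings the result back to 28 days. Read so, the formula returns the intended value at every X. But this reading has to override two written definitions at once, the monthly scale and formula A's denominator, and overriding only one still gives a wrong value.

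Reading B can also be called only half literal, because SAP 6.1.2 describes the numerator as observed data while imputed days are being added to it. It is, however, what 6.1.4 asks for. Its most extreme results would be noticed on inspection. Reading A is the quieter risk, since its results look plausible.

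The following points stand as limits:

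- The size rests on assumptions. The planned 10% discontinuation for all reasons is about 0.10 x 43.5 = 4.35 patients in the arm, so four qualifying patients is a high case.
- The paragraph in 6.1.4 is headed for ANCOVA and MMRM, while the responder endpoint uses a CMH test. The closing note and the reference in 6.3.1 still bring that endpoint in.
- The MMRM sensitivity analysis uses 4-week windows, which are free of the one-third fault. A gap between the two analyses might reveal the error, but might equally be taken for sensitivity to missing data.
- X counts recorded days, not the day of exit, so (84-X) also fills earlier diary gaps. That is the SAP's own term and does not affect the two faults.

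**Conclusion.** The concern holds. As written, the 12-week rule in SAP 6.1.4 does not deliver the placebo values promised in SAP 1.6 and Protocol 9.5.5.1, and it leaves more than one value open for the same patient.

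The fault is confined to fremanezumab patients who leave for the three named reasons. It reaches the primary ANCOVA and the 12-week responder endpoint. In the illustrations, two to four such patients move the arm mean by between roughly 0.1 and 0.7 days, in a direction set by the programming choice and, at higher X, by the patient's own rate. That is up to about a third of the planned 2.0-day difference (0.74/2.0 = 0.37), and with no qualifying patients it is nothing. The inconsistency itself does not depend on the assumed rates. Because it sits in the primary derivation and costs almost nothing to remove, it should be corrected before unblinding.

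**What to change.** Replace the 12-week part of SAP 6.1.4 with one explicit formula for these patients:

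12-week monthly average = [observed headache days + (84-X) x (placebo monthly average/28)] / 84 x 28

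State that the imputed total is not passed through formula A with X as the denominator. State also that the imputation window is the nominal 84 days. This is needed because SAP 6.2.1 says "The 12-week period is the period from administration of the first dose of IMP to the EODBT as defined in Section 4.4", and under 4.4 that end point is the early termination visit for patients who leave early and do not enter the open-label period.

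As a secondary tidy-up, for which no effect was computed, use one donor group: SAP 1.6 takes all patients assigned to placebo, while 6.1.4 takes those who completed the study.

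The cost is SAP wording and one line of derivation code before unblinding, with no new data. The estimate may move either way, or not at all, depending on how the present text would have been programmed and on how many patients qualify.
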